3.2.3. TTR by ICR/INV

Time to Response (TTR) based on ICR/derived investigator assessments is defined, for participants with a confirmed objective response, as the time from the date of first dose to the first documentation of objective response (CR or PR) which is subsequently confirmed. For participants whose OR proceeds from PR to CR, the onset of PR is taken as the onset of response.

3.2.4. IC-TTR by ICR/INV

Time to Intra-Cranial Response (IC-TTR) based on ICR/derived investigator assessments is defined, for participants with a confirmed intra-cranial objective response, as the time from the date of first dose to the first documentation of objective intra-cranial response (CR or PR) which is subsequently confirmed. For participants whose IC-OR proceeds from PR to CR, the onset of PR is taken as the onset of response.

3.2.5. DoR by ICR/INV

Duration of Response (DoR) based on ICR/ derived investigator assessment is defined, for participants with a confirmed objective response, as the time from first documentation of objective response (CR or PR whichever is earlier) to the date of first documentation of PD or death due to any cause, whichever occurs first. The censoring rules for DOR are identical to those presented for PFS in section 6.2.7.

3.2.6. IC-DoR by ICR/INV

Duration of Intra-Cranial Response (IC-DoR) based on ICR/ derived investigator assessment is defined, for participants with a confirmed objective intra-cranial response, as the time from first documentation of objective intra-cranial response (CR or PR whichever is earlier) to the date of first documentation of PD in brain or death due to any cause, whichever occurs first. The censoring rules for DOR are identical to those presented for PFS in section 6.2.7.

3.2.7. PFS by ICR/INV

Progression Free Survival (PFS) is defined as the time from date of first dose to the date of the first documentation of PD (per RECIST v1.1 based on ICR/derived investigator assessment) or death due to any cause, whichever occurs first. Refer to section 6.2.7 for details on censoring rules.

3.2.8. TTP by ICR/INV

Time To Progression (TTP) is defined as the time from date of first dose to the date of the first documentation of PD (per RECIST v1.1 based on ICR/derived investigator assessment). Refer to section 6.2.8 for details on censoring rules.

DMB02-GSOP-RF02 4.0 Statistical Analysis Plan Template 01-Nov-2018 PFIZER CONFIDENTIAL Page 13 TMF Doc ID: 98.03

3.3. Other Endpoints

Not Applicable

3.4. Baseline Variables

The date of first dose (start date) of study treatment is the earliest date of non-zero dosing of the study drug. The date of last dose of study treatment is the latest date of non-zero dosing of the study drug.

No windowing will be applied when defining baseline, except as noted in Section 5.2.8 for tumor assessments. Any deviations from the protocol specified window will be documented as protocol deviations. A separate definition of adequate baseline will be provided for tumor assessment related efficacy endpoints.

For efficacy analyses and baseline characteristics associated with tumor assessments the last assessment prior to treatment start date will serve as the baseline assessment.

For Adverse Events the last assessment performed on or prior to date of the first dose of study treatment will serve as the baseline assessment. If there are no observations meeting these criteria, then baseline is considered missing.

3.5. Safety Endpoints

Safety endpoints in this study will be limited to Adverse Events and maximum Weight increase from baseline.

3.5.1. Adverse Events

Adverse Events will be summarized based on the on-treatment period unless otherwise specified.

On-treatment is defined as the time from the first dose of study treatment through end of safety follow-up period, ie at least 28 days, and no more than 35 days after discontinuation of treatment, or start of new anti-cancer therapies (follow up systemic therapy, follow up radiation therapy or follow-up surgery), whichever occurs first. Adverse events occurring on the same day as the first dose of study treatment will be considered to have occurred during the on-treatment period.

Adverse events collected outside the on-treatment period as described above will be listed but not summarized. All adverse events with onset date on or after start of a new anti-cancer drug therapy will also be listed on a separate display.

An adverse event is considered treatment emergent (TEAE) when the onset date is greater or equal to the treatment period start date.

All Adverse Events (AEs) will be coded using the Medical Dictionary for Regulatory Activities (MedDRA). The investigator will classify the severity of AEs using the CTCAE v4.03.

DMB02-GSOP-RF02 4.0 Statistical Analysis Plan Template 01-Nov-2018 PFIZER CONFIDENTIAL Page 14 TMF Doc ID: 98.03

Adverse Events of Special Interest (AESI)

AESIs include events such as HYPERCHOLESTEROLEMIA and HYPERTRIGLYCERIDEMIA, EDEMA, PERIPHERAL NEUROPATHY, COGNITIVE EFFECTS, MOOD EFFECTS, SPEECH EFFECTS, Weight gain, VISION DISORDER, Liver tests increased, QT interval prolongation, Interstitial lung disease/Pneumonitis, Atrioventricular (AV) block, and Pancreatitis. These events will be defined based on a list of MedDRA Preferred Terms specified in the Safety Review Plan for lorlatinib. A final list will be provided to programming prior to database release.

3.5.2. Vital Signs – Weight

Weight will be summarized based on the on-treatment period.

Assessments of weight which occur on the same day as the first dose of study treatment will be considered baseline assessments (see section 3.4 for the definition of baseline).

4. ANALYSIS SETS (POPULATIONS FOR ANALYSIS)

For purposes of analysis, the following populations are defined:

Population	Description
Enrolled	All participants who sign the ICF
Intent to Treat (ITT)/Safety	All enrolled participants who take at least 1 dose of lorlatinib
Per Protocol Population: Participants with CNS metastases based on ICR	Subset of the ITT analysis set including only participants with CNS metastases at study entry (i.e. with Lesions having Disease Site=Brain) according to ICR
Per Protocol Population: Participants with CNS metastases based on Investigator Assessment	Subset of the ITT analysis set including only participants with CNS metastases at study entry (i.e. with Lesions having Disease Site=Brain) according to Investigator Assessment

Data for all participants will be assessed to determine if participants meet the criteria for inclusion in each analysis population prior to unblinding and releasing the database and classifications will be documented per standard operating procedures.

5. GENERAL METHODOLOGY AND CONVENTIONS

The primary analysis of objective tumor response based on ICR assessment will be performed at study participant data set release after 12 calendar months after the LPFV date in the study (as per End of Trial protocol definition).

Participants who still experience clinical benefit at the End of Trial will discontinue from the study and continue treatment per standard of care.

DMB02-GSOP-RF02 4.0 Statistical Analysis Plan Template 01-Nov-2018 PFIZER CONFIDENTIAL Page 15 TMF Doc ID: 98.03 The study will be reported using CDISC.

5.1. Hypotheses and Decision Rules

5.1.1. Hypotheses and Sample Size

According to literature, platinum-based doublet chemotherapy in participants with ALK + NSCLC refractory to second generation TKIs has an objective response rate of approximately 30%. Setting as target for lorlatinib a response rate of about 43% (as observed in cohort EXP-3B of phase 2 portion of study B7461001), a sample size of 60 participants would result in an exact two-sided 95% CI of the ORR with lower limit of the CI greater than 30%. In order to compensate for a potential 15% drop out rate (participants with death prior to first post-baseline assessment, inadequate baseline assessment, new anti-cancer therapy started prior to first post-baseline assessment, post-baseline disease assessments missing), the overall sample size for the study is set to 70 participants.

5.1.2. Decision Rules

The study will be considered to have met its primary endpoint if the lower limit of the 95% confidence interval around the estimated ORR excludes 30%.

5.2. General Methods

5.2.1. Data handling after the cut-off date

Data after the cut-off date may not undergo the cleaning process and will not be displayed in any listings or used for summary statistics, statistical analyses or imputations

5.2.2. Definition of study day

Start day of study treatment is the day of the first dose of study treatment.

The study day for assessments occurring on or after the first dose of study treatment (eg, adverse event onset) will be calculated as:

Study day = Date of the assessment/event - start date of study treatment + 1.

The study day for assessments occurring prior to the first dose of study treatment (eg, baseline characteristics, medical history) will be negative and calculated as:

Study day = Date of the assessment/event -start date of study treatment.

For efficacy endpoints and for tumor assessment the study day will be calculated with respect to the date of study treatment start.

The study day will be displayed in all relevant data listings.

5.2.3. Definition of Cycle and Cycle Day

Cycle start and end dates are derived per patient. Treatment will be dispensed at the beginning of every 21-day cycle.

DMB02-GSOP-RF02 4.0 Statistical Analysis Plan Template 01-Nov-2018 PFIZER CONFIDENTIAL Page 16 TMF Doc ID: 98.03

- For Cycle X, the actual cycle start date for each subject is the earliest start date of dosing (dose>0 at that visit) in Cycle X visit CRF exposure page
- For all but the last cycle,
 - actual cycle stop date is calculated as the start date of the next cycle minus one day.
 - actual cycle duration is calculated from Day 1 of a cycle to the day prior to Day 1 of the next cycle, as follows: Actual Cycle Duration (weeks) = (cycle stop date cycle start date + 1) / 7
- For the last cycle, actual cycle duration is calculated as follows:
 - Actual Cycle Duration (weeks) = (last date of study treatment- cycle start date + 1) /7

The cycle day will be calculated as:

• Cycle day = Date of the assessment/event – cycle start date + 1.

5.2.4. Date of last contact

The date of last contact will be derived for patients not known to have died at the data cutoff date using the latest complete date (i.e. imputed dates will not be used in the derivation) among the following:

- All patient assessment dates e.g. tumor assessments
- Start and stop dates of concomitant therapies including non-drug treatments or procedures
- Start and end dates of anti-cancer therapies administered after study treatment discontinuation including systemic therapy, radiation, and surgeries,
- AE start and end dates
- Date of first and last dose
- Vital sign weight assessment dates
- Date of discontinuation on disposition CRF pages (do not use if reason for discontinuation is lost to follow-up or death).

Only dates associated with actual examinations of the patient will be used in the derivation. Dates associated with a technical operation unrelated to patient status such as the dates data were entered into the CRF will not be used.

Assessment dates after the data cutoff date will not be applied to derive the last contact date.

DMB02-GSOP-RF02 4.0 Statistical Analysis Plan Template 01-Nov-2018 PFIZER CONFIDENTIAL Page 17 TMF Doc ID: 98.03

5.2.5. Measurable Disease

A patient will be considered to have measurable disease if there is at least one target lesion identified at baseline meeting the following criteria:

- Non lymph node lesions with longest diameter ≥ 10 mm by CT scan,
- Non lymph node lesions with longest diameter ≥ 10 mm caliper measurement by clinical exam,
- CNS lesions with longest diameter ≥5 mm provided by gadolinium contrast enhanced MRI perfomed with contingent slices of 1 mm, or
- Lymph nodes with short axis ≥ 15 mm when assessed by CT.

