LVEF Assessment	X		Echocardiogram or MUGA will be performed. During study treatment additional assessments may be performed as clinically indicated and according to lorlatinib product information.
			For France and Germany, a transthoracic echocardiogram (TTE) will be performed every 6 months (± 2 weeks) during treatment, and only at the end of treatment visit if the previous assessment was > 1 month. Pulmonary arterial pressure (PAP) will be assessed.
Registration	·		
Registration		(X)	Registration will be within 2 days prior to study treatment start.
Tumor Assessments			
CT and MRI Scan or Equivalent	X		Tumor assessments will include all known or suspected disease sites. CT or MRI scans of Chest Abdomen Pelvis [CAP] and MRI of the brain will be performed at screening. Bone scans (or bone MRI if preferred by investigator) will be performed at baseline for all participants and repeated every 12 weeks on study only if evidence of bone metastases is observed at baseline.

Visit Identifier	Screening*	Cycle 1 (21 days)	Notes  *to be obtained within 28 days prior to registration	
Visit Window	≤28 days	Day 1 (±1 day)	(X) refer to specific footnote when the measurement may be optional /repeat measurement might not be required.	
Cerebrospinal fluid if leptomeningeal/carcinomatous meningitis [LM/CM] disease is present	X		CSF is mandatory for participants who have asymptomatic radiologically suspected leptomeningeal disease (LM) or carcinomatous meningitis (CM) but negative spinal fluid.	
Other Clinical Assessments	Other Clinical Assessments			
Adverse Events	X	X	For AEs and SAEs, the active reporting period to Pfizer or its designated representative begins from the time that the participant provides informed consent, which is obtained prior to the participant's participation in the study through and including a minimum of 28 calendar days after the last administration of the study intervention. Refer to Section 8.3.1 for all specifications.	
Concomitant medications and non- drug supportive interventions	X	X		

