#### 8.1. Efficacy Assessments

#### 8.1.1. Tumor Assessments

Tumor assessments will include all known or suspected disease sites. Computed tomography (CT) or MRI scans of Chest Abdomen Pelvis (CAP) and MRI of the brain will be performed at screening. Gadolinium contrast enhanced MRI must be used for assessment of CNS lesions with contingent slices of 1 mm for lesions 5 mm - 10 mm in size, 5 mm for lesions greater than 10 mm. Bone scans (or bone MRI if preferred by investigator) will be performed at baseline for all participants and repeated every 12 weeks on study only if evidence of bone metastases is observed at baseline (however, if a participant has bone involvement, assessment of those sites via appropriate modality is required every 6 weeks ±1 week up to 24 months or progressive disease whichever occurred first). For all tumor assessments, the method of assessment that was used at baseline should be the same method used throughout the study. CT and MRI scans to be done at every 6 weeks  $\pm 1$  week up to approximately 24 months (cycle 35) and then as per local clinical practice. Tumor assessment should be repeated at the end of treatment if more than 6 weeks have passed since the last evaluation. Tumor assessment should not be repeated at the end of treatment if progression occurs when the participant has shifted to the local clinical practice. Moreover, radiological tumor assessments will be conducted whenever disease progression is suspected (eg, symptomatic deterioration).

Assessment of response will be made using RECIST version 1.1 (Appendix 5). Confirmation of response will be required at least 4 weeks after initial response is observed.

All participants' files and radiologic images must be available for source verification and for peer/independent central radiology review as determined by the sponsor. Instructions for submission of these images will be provided in the Study Reference Manual.

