### Special Considerations Regarding Specific Lesions

#### **Bone lesions:**

- Bone scan, positron emission tomography (PET) scan or plain films are not considered adequate imaging techniques to measure bone lesions. However, these techniques can be used to confirm the presence or disappearance of bone lesions.
- Lytic bone lesions or mixed lytic-blastic lesions, with identifiable soft tissue components, that can be evaluated by cross sectional imaging techniques such as CT or MRI can be considered as measurable lesions if the soft tissue component meets the definition of measurability described above.
- Blastic bone lesions are non-measurable.

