3. ENDPOINTS AND BASELINE VARIABLES: DEFINITIONS AND CONVENTIONS

3.1. Primary Endpoint

3.1.1. Confirmed OR by ICR

Objective Response (OR) based on ICR assessment is defined as complete response (CR) or partial response (PR) according to RECIST v1.1 from date of first dose until documented PD or start of new anti-cancer therapy without regard to discontinuation from treatment. Both CR and PR must be confirmed by repeat assessments performed no less than 4 weeks after the criteria for response are first met.

Participants without a CR or PR or with death prior to first post-baseline assessment, inadequate baseline assessment, new anti-cancer therapy started prior to first post-baseline assessment, and all post-baseline disease assessments missing will be considered as non-responders.

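### SAP 5.2.5 omits MRI as a route to extracranial measurable disease, so a participant with only MRI-measured targets would count as a non-responder in the primary ORR

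*SAP*

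**What the plan says.** **SAP 5.2.5** calls a patient measurable if at least one baseline target lesion meets one of four lines:

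- The first line is the CT route outside the nodes: "Non lymph node lesions with longest diameter ≥ 10 mm by CT scan".
- The second line is the only route without imaging: "Non lymph node lesions with longest diameter ≥ 10 mm caliper measurement by clinical exam".
- The third line covers the brain and is the only one to name MRI: "CNS lesions with longest diameter ≥5 mm provided by gadolinium contrast enhanced MRI perfomed with contingent slices of 1 mm, or".
- The fourth line covers nodes and again names one modality: "Lymph nodes with short axis ≥ 15 mm when assessed by CT".

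**SAP 5.2.8** makes this a condition of an adequate baseline. **SAP 3.1.1**, repeated in 6.1.1, sets the consequence: participants with "inadequate baseline assessment, new anti-cancer therapy started prior to first post-baseline assessment, and all post-baseline disease assessments missing will be considered as non-responders". The denominator is the ITT set (6.1.1).

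**Protocol imaging rules.** The Schedule of Activities (1.3.1) states: "CT or MRI scans of Chest Abdomen Pelvis [CAP] and MRI of the brain will be performed at screening". Section 8.1.1 says the same and asks that the baseline method be kept throughout. For CNS lesions, 8.1.1 specifies "contingent slices of 1 mm for lesions 5 mm - 10 mm in size, 5 mm for lesions greater than 10 mm".

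**Protocol Appendix 5.** The general thresholds (10 mm, and 15 mm short axis for nodes) are worded for CT. Lytic or mixed bone lesions with a soft-tissue component "that can be evaluated by cross sectional imaging techniques such as CT or MRI can be considered as measurable lesions", provided the soft tissue meets the measurability definition. The text on recording measurements describes nodal planes on MRI, but still states the 15 mm nodal criterion by CT.

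**The concern.** The protocol lets a site image the body by MRI and then asks it to stay with MRI. The SAP's measurability definition has no line for an extracranial lesion measured that way. The definition does more than describe baseline characteristics: it decides who can be a responder. A program written from the SAP would set aside a confirmed response read by central review if the participant had no target meeting 5.2.5.

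The same participant would be censored at first dose for PFS, unless death occurs within 98 days (Table 2, footnote a), and for TTP (Table 4). The error runs in one direction, towards a lower ORR, and depends on the scanner used rather than on the tumour.

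**Working it through.** **1. Chain of rules**

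| Step | Source | Result for a participant whose targets are all on body MRI |
|---|---|---|
| Body imaging by CT or MRI | Protocol 8.1.1, SoA | Complies |
| A qualifying target lesion | SAP 5.2.5 | None: no CT, no caliper, no brain target meeting the CNS line |
| Adequate baseline | SAP 5.2.8 | No |
| Primary endpoint | SAP 3.1.1, 6.1.1 | Non-responder, kept in the denominator |

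One qualifying target is enough. A participant with one chest target on CT and the rest on MRI is unaffected.

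**2. The plan's own figure.** Inputs from SAP 5.1.1 and 5.1.2: reference ORR 30%, target about 43%, n = 60 raised to 70 for 15% drop-out, and success if the lower limit of the exact two-sided 95% CI exceeds 30%. The Clopper-Pearson lower limit for x responders in n is the 0.025 quantile of Beta(x, n − x + 1).

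- 26/60 = 43.3%: CI 30.6% to 56.8%. 25/60 has a lower limit of 29.1%. The stated n = 60 reproduces, with 26 as the minimum.
- Inflation: 60/0.85 = 70.6, rounded up to 71; 60 × 1.15 = 69. The stated 70 lies between.
- At n = 70: 30/70 (42.9%) has a lower limit of 31.1% and succeeds; 29/70 (41.4%) has 29.8% and fails. Success needs at least 30 responders.

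**3. Effect of m participants forced to non-response.** The documents give no m, so it is an assumption.

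- Expected ORR = 0.43 × (70 − m)/70; expected loss = 0.43 × m/70.
- Largest loss, if all m are true responders = m/70.
- Chance of success = P(X ≥ 30), X ~ Binomial(70 − m, 0.43).

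| m | Expected ORR | Expected loss (points) | Largest loss (points) | Chance of success |
|---|---|---|---|---|
| 0 | 43.0% | 0 | 0 | 55.5% |
| 1 | 42.4% | 0.6 | 1.4 | 51.4% |
| 2 | 41.8% | 1.2 | 2.9 | 47.2% |
| 3 | 41.2% | 1.8 | 4.3 | 43.0% |

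These rows assume no other non-evaluable participants. If ten others are non-evaluable, roughly the plan's allowance, and count as non-responders, the chance is P(X ≥ 30) with X ~ Binomial(60 − m, 0.43): 16.7% at m = 0, 13.9% at m = 1 and 9.2% at m = 3.

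**4. CNS line**

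| Brain lesion | Protocol 8.1.1 | SAP 5.2.5 | Agreement |
|---|---|---|---|
| 5 to 10 mm | 1 mm slices | 1 mm slices | Yes |
| Above 10 mm | 5 mm slices | 1 mm slices | No |

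Read literally, a 20 mm brain lesion scanned as the protocol specifies does not qualify, while a 6 mm one does. For the primary ORR this matters only when no extracranial target qualifies, and inclusion criterion 4 requires every participant to have a measurable extracranial target.

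**The case against.** **The CT wording did not start in the SAP.** Appendix 5 states its general thresholds by CT, and SAP 5.2.5 largely repeats them. One could argue that a participant with only body-MRI targets does not meet inclusion criterion 4, so the SAP misclassifies nobody. This stands in part. The conflict is also inside the protocol, between 8.1.1 and the Appendix 5 thresholds, and that participant's eligibility is ambiguous. It does not dispose of the point: Appendix 5 names MRI for bone soft-tissue lesions, and 5.2.5 has no matching route.

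**A reader might infer that every participant imaged by MRI becomes a non-responder.** The documents do not support that. Measurability is judged per patient on a single lesion, so only those with no qualifying target are at risk.

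**A reader might infer that the slice rule removes the largest brain lesions from the intracranial analysis.** Nothing says so. The intracranial sets (SAP section 4) take any participant with a brain lesion and require no measurability. Section 5.2.5 classifies patients; it does not choose target lesions or remove them from the sum of diameters. SAP 3.2.2 does count an inadequate baseline as intracranial non-response, but nothing states that adequacy is judged again on brain lesions alone.

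**The one-responder flip is a property of the success boundary.** Any single lost responder turns 30/70 into 29/70. The planned drop-out allowance also matters far more: 26 responders among 60 evaluable become 26/70, with a lower limit of 25.9%, which fails whatever 5.2.5 says. Both remarks are correct, and they limit how much weight the success probabilities can carry.

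**Conclusion.** The mismatch is certain as a matter of text. As written, SAP 5.2.5, 5.2.8 and 3.1.1 together make a participant without a qualifying target a non-responder because the lesions were measured on body MRI, which 8.1.1 allows.

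The size is uncertain. The number affected is unknown and may be zero. The expected loss of 0.6 to 1.8 points rests on an assumed 1 to 3 of 70 responding at the 43% target; the 1.4 to 4.3 point figures apply only if every one of them is a true responder. The fall in the chance of success also assumes no other non-evaluable participants.

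The CNS slice discrepancy is real above 10 mm. It does not by itself cause primary non-response, and no loss of IC-ORR is shown.

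This is worth correcting before database lock, because the alternative is ruling on individual participants after their responses are known.

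**What to change.** In SAP 5.2.5:

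- Accept non-nodal lesions of at least 10 mm by CT or MRI, and nodes of at least 15 mm short axis by CT or MRI. Keep the caliper line.
- Replace the single CNS slice condition with the two tiers in protocol 8.1.1.

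In SAP 3.2.2 or 6.2.2, add one sentence saying whether an adequate baseline for IC-OR requires a measurable brain lesion.

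At the next protocol amendment, align the measurable-lesion list and the nodal criterion in Appendix 5 with 8.1.1.

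Cost: one SAP paragraph and one sentence now, with no new scans or data. The Appendix 5 change is protocol text and needs an amendment with IRB/IEC approval (protocol 10.1.1), so it can wait for one made for other reasons. Until then the SAP would be wider than the general thresholds in Appendix 5, and it should say that it follows 8.1.1.
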